## 11.1 Risk and Quality Tolerance Limits

Perceived risks and quality tolerance limits (QTLs) will be identified and documented in the Protocol Risk Evaluation Plan before the start of the study.

The Sponsor will review risk control measures periodically to ascertain whether the implemented quality management activities remain effective and relevant. The quality management approach and any important deviations from the predefined QTLs (and remedial actions adopted) will be described in the CSR.

## **11.2 Protocol Adherence and Deviations**

The Investigator and site personnel should conduct the study in compliance with the protocol and should use continuous vigilance to identify and report protocol deviations.

A protocol deviation is any change, divergence, or departure from the study design or procedures defined in the protocol that may be on the part of the Investigator, the site personnel, or the patient.

Important protocol deviations are a subset of protocol deviations that may significantly impact the completeness, accuracy, and/or reliability of the study data or that may significantly affect a patient's rights, safety, or well-being. For example, important protocol deviations may include enrolling patients in violation of key eligibility criteria designed to ensure a specific patient population or failing to collect data necessary to interpret primary endpoints, as this may compromise the scientific value of the study.

The Investigator should not implement any deviation from the protocol without agreement from the Sponsor and prior review and approval from the IRB/IEC of an amendment, except where necessary to eliminate an immediate hazard to a study patient, or when the change involves only logistical or administrative aspects of the study, such as a change in a monitor or phone number.

In the event of an important protocol deviation, the Investigator will discuss the deviation with the Sponsor's Medical Monitor and will come to an agreement as to whether the patient should be withdrawn from the study due to the important protocol deviation.

# **12 AMENDMENTS**

Protocol modifications, except those intended to reduce immediate risk to study patients, may be made only by the Sponsor. A protocol change intended to eliminate an apparent immediate hazard to patients should be implemented immediately.

Any permanent change to the protocol must be handled as a protocol amendment. The written amendment must be submitted to the IRB/IEC, and the Investigator must await approval before implementing the changes. The Sponsor will submit protocol amendments to the appropriate regulatory authorities for approval.

The current version of the ICF will require similar modification if the IRB/IEC, Investigator, and/or Sponsor, judge the amendment to the protocol to substantially change the study design and/or increase the potential risk to the patient and/or impact the patient's involvement as a study patient. In such cases, the ICF will be renewed for enrolled patients before their continued participation in the study.

# **13 STUDY REPORT AND PUBLICATIONS**

This study will be registered on ClinicalTrials.gov in accordance with applicable laws or publication policy and may also be registered on other publicly accessible websites, such as EudraCT (EU Drug Regulating Authorities Clinical Trials), as necessary.

Two CSRs will be prepared. The first CSR will contain all results from this study, except for the results of genetic analyses, which will be reported separately. The Sponsor is responsible for preparing and providing the appropriate regulatory authorities with the CSRs according to the applicable regulatory requirements. The Sponsor should ensure that the CSRs meet the standards of the ICH Guideline for Structure and Content of Clinical Study Reports (ICH E3).

The publication policy of the Sponsor is discussed in the Investigator's clinical trial agreement.

## **14 STUDY START AND TERMINATION**

The study start date is the date on which the first patient provides informed consent.

The end of the study is defined as the last patient's last assessment.

Both the Sponsor and the Investigator reserve the right to terminate the study or the participation in the study at an Investigator's site at any time. In terminating the study, the Sponsor and the Investigator will assure that adequate consideration is given to the protection of the patients' interests.

If the study is prematurely terminated or suspended for any reason, the Sponsor/Investigator/site personnel should promptly inform the study patients and should assure appropriate therapy and follow-up for the patients. Where required by the applicable regulatory requirements, the IRB/IEC should be informed promptly and be provided with a detailed written explanation of the termination or suspension.

If the Investigator terminates or suspends a study without prior agreement of the Sponsor, the Investigator should inform the site personnel. The Investigator/site personnel should promptly inform the Sponsor and the IRB/IEC. The Investigator/site personnel should also provide the Sponsor and the IRB/IEC a detailed written explanation of the termination or suspension.

# **15 CONFIDENTIALITY**

All information generated in this study is considered highly confidential and must not be disclosed to any person or entity not directly involved with the study unless prior written consent is gained from the Sponsor. However, authorized regulatory officials, IRB/IEC personnel, the Sponsor and its authorized representatives are allowed full access to the records.

All study patients must be informed that their personal study-related data will be used by the Sponsor in accordance with local data protection law. The level of disclosure must also be explained to the patient, who will be required to give consent for their data to be used as described in the ICF. The patients must be informed that their medical records may be examined by auditors or other authorized personnel appointed by the Sponsor, by appropriate IRB/IEC members, and by inspectors from regulatory authorities. In case of any data security breach, this will be reported to authorities in line with local requirements.

Identification of patients and eCRFs shall be by unique patient identification numbers (such as screening or randomization numbers) only. All personal identifiers according to applicable regulations (eg, name, phone number) must be redacted permanently by the site personnel and replaced with the patient's unique identification number in all records and data before transfer to the Sponsor (or designee).

All personal details will be treated as confidential by the Investigator and staff at ICON.

#### 17.2 APPENDIX II – Detection and Management of Suspected or Confirmed Cases of Drug-Induced Liver Injury

Particular attention will be given to the detection and management of suspected or confirmed cases of DILI.

If any of the following laboratory results or clinical signs or symptoms are obtained during the study, the Investigator will instruct the patient to return to the study center within 24 to 48 hours of receipt of the laboratory test results to undergo a retest.

- AST or ALT  $\geq 3 \times ULN$
- AST or ALT >2×Baseline
- Total bilirubin >2×ULN
- INR >1.5 (except for patients on anticoagulant therapy)
- Clinical signs or symptoms that are, in the opinion of the Investigator, consistent with hepatitis (such as right upper quadrant discomfort, fever, fatigue, nausea, vomiting, jaundice, rash, or eosinophilia >5%) or drug-induced hepatotoxicity. Isolated eosinophilia >5% without clinical signs or symptoms that are consistent with hepatitis or hepatotoxicity by the Investigator's medical judgment, should not be considered suspected DILI (sDILI). Retesting of eosinophilia (>5%) will only be required in case this is observed in combination with at least one of the other criteria listed above.

Baseline values for liver tests (ALT, AST, and total bilirubin) are determined by averaging the values obtained at Screening and Baseline/Day 1 to obtain the arithmetic mean.

The results of the Test and Retest will be checked to determine if they meet the criteria in A or B, which are based on the patient's ALT and AST levels at Baseline, or C below:

#### 17.2.1 Criteria for Close Monitoring of Liver Biochemistry and IMP Action

- A) For patients with ALT and/or AST <ULN at study start (Baseline Values), unless an alternative cause for the combination of laboratory abnormalities is immediately apparent (and documented) at the time of the laboratory test elevations in the opinion of the Investigator, close monitoring for sDILI (as described in Appendix II, Section 17.2.2) will be performed in patients with any of the following criteria (all confirmed by repeat testing):
  - a. ALT or AST  $>3 \times ULN$
  - b. Total bilirubin >2×ULN
  - c. INR >1.5 (except for patients on anticoagulant therapy)

- d. Clinical signs or symptoms that are, in the opinion of the Investigator, consistent with hepatitis (such as right upper quadrant discomfort, fever, fatigue, nausea, vomiting, jaundice, rash, or eosinophilia >5% provided the latter is in combination with any of the other criteria listed under A-a, b, c or d).
- B) For patients with ALT and/or AST between ≥ULN and <3×ULN at study start (Baseline Values), unless an alternative cause for the combination of laboratory abnormalities is immediately apparent at the time of the laboratory test elevations in the opinion of the Investigator (and documented), close observation for DILI (as described in Appendix II, Section 17.2.2) will be performed in patients with any of the following criteria (all confirmed by repeat testing):

  - a. ALT or AST >2×Baseline at any time (see Figure 2 for illustration)
  - b. Total bilirubin  $>2 \times ULN$
  - c. INR >1.5 (except for patients on anticoagulant therapy)
  - d. Clinical signs or symptoms that are, in the opinion of the Investigator, consistent with hepatitis (such as right upper quadrant discomfort, fever, fatigue, nausea, vomiting, jaundice, rash, or eosinophilia >5% provided the latter is in combination with any of the other criteria listed under A-a, b, c or d).

During the close monitoring period in A and B, IMP can be continued, unless:

[figure not shown]
- The patient is symptomatic in addition to having elevated laboratory parameters
- Close Monitoring is not possible
- Criteria C of Appendix II (see below) are met and no other cause for laboratory abnormalities is clinically apparent and documented by the Investigator in the study documents
- At the discretion of the Investigator
- **C)** For patients meeting any of the following events, IMP will be discontinued when no other cause for the combination of laboratory abnormalities is immediately apparent:
  - a. ALT or AST  $>5 \times$  Baseline
  - b. ALT or AST  $>10 \times ULN$
  - c. ALT or AST >3×Baseline (see Figure 3 for illustration) with 1 or more of the following:
    - i. Total bilirubin >2×ULN

- ii. Total bilirubin >1.5×Baseline and >ULN
- iii. INR >1.5 (except for patients on anticoagulant therapy)
- iv. Appearance of clinical signs or symptoms that are, in the opinion of the Investigator, consistent with drug-induced hepatotoxicity
- d. ALT or AST >Baseline with any 2 or more of the following:
  - i. Total bilirubin >2×ULN or 1.5×Baseline
  - ii. INR>1.5 (except for patients on anticoagulant therapy)
  - iii. Appearance of clinical signs or symptoms that are, in the opinion of the Investigator, consistent with drug-induced hepatotoxicity

If the above criteria in **C** are met, the Investigator will instruct the patient to discontinue IMP administration and return to the study center within 2 days of receipt of the laboratory test results to undergo a retest and additional investigations (ie, close monitoring) to assess for sDILI. IMP cannot be reintroduced.

[figure not shown]
Any suspected or confirmed DILI event, defined as events meeting the criteria in A, B, or C above, will be closely monitored by the Investigator and the IDMC and reported to the Sponsor as an AESI following the same procedure as for SAEs.

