#### 7.1.5 Adverse Events of Special Interest

The AESIs for this study are DILI, anemia, and hypothyroidism.

AESIs of DILI will be defined as any DILI event that meets the criteria in **A**, **B**, or **C** of Appendix II. Please refer to Section 5.3.2.1 and Appendix II for details regarding the detection and management of cases of DILI.

AESIs of anemia will be defined as CTCAE Grade  $\geq 2$  anemia AND absolute reticulocyte counts of <50% of the Baseline value, which is confirmed by repeat testing. Please refer to Section 5.3.2.2 for details regarding the detection and management of potential cases of bone marrow toxicity.

AESIs of hypothyroidism will be defined as TSH levels of  $\geq 10$  mIU/L, which is confirmed by repeat testing at the central laboratory (ie, TSH  $\geq 10$  mIU/L and reduced free T4). Please refer to Section 5.3.2.3 for details regarding the detection and management of hypothyroidism. The AESI should be reported by the investigative site to the ICON Drug Safety Center within 24 hours of learning about the event by completing the paper safety report form and sending it via email or fax. The documentation and processing of AESIs is further detailed in the Investigator Site File.

The AESIs will be adjudicated by the Adjudication Committee (see Section 9.4.1).

Investigators will indicate on the relevant Adverse Event eCRF page if the event meets the criteria for an AESI. If the event meets the criteria for an AESI, the Investigator will inform the Sponsor (or designee) of the AESI utilizing the safety report form (refer to the SAE contact information at the beginning of this protocol) and will then complete the Adjudication Event eCRF.

Please refer to the Investigator adjudication manual for further information.

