### 17.2.2 Close Monitoring

- 1. Monitor patient twice or 3 times weekly until liver biochemistries (ALT, AST, ALP, total bilirubin), and coagulation profile (INR) resolve, stabilize or return to within Baseline values. Additional tests (eg, conjugated bilirubin) should also be obtained, as appropriate, at the discretion of the Investigator.
- 2. Monitor liver biochemistries and coagulation profile once a week or less according to the Investigator's judgment if the abnormalities stabilize, resolve or return to within Baseline values, or IMP has been discontinued and the patient is asymptomatic.
- 3. Close Monitoring can be stopped based on the Investigator's clinical judgment once the abnormalities stabilize, resolve or return to within Baseline values; or when there is an alternative documented cause to explain the deterioration.
- 4. Obtain a detailed history for symptoms assessment: appearance or worsening of clinical symptoms of hepatitis (such as right upper quadrant discomfort, fever, fatigue, nausea, vomiting, jaundice, rash, or eosinophilia >5%). If a patient is symptomatic in addition to having elevated laboratory parameters, the drug must be discontinued immediately, and a suspected DILI evaluation must be performed.
- 5. Obtain a more detailed history of prior or concomitant diseases.

- 6. Obtain a history for concomitant medications, acetaminophen, dietary supplements, herbal remedies, other over-the-counter medications, recreational drug use, and special diets.
- 7. If possible, quantify the alcohol consumption to assess for alcoholic hepatitis.
- 8. Obtain a history of exposure to environmental chemical agents.
- 9. If INR is also elevated, a trial of intravenous vitamin K administration may be considered, especially in cholestatic patients.

Follow-Up procedures for patient(s) who meet suspected DILI evaluation criteria in A, **B**, or **C** (laboratory analyses are performed at the central laboratory):

Viral hepatitis serology including:

- 1. Hepatitis A IgM antibody.
- 2. Hepatitis B surface antigen and Hepatitis B Core Antibody (IgM).
- 3. Hepatitis C RNA.
- 4. Hepatitis E IgM antibody.
- 5. Cytomegalovirus IgM antibody.
- 6. Epstein-Barr viral capsid antigen IgM antibody (or if unavailable, obtain heterophile antibody or monospot testing); however, IgM antibodies must be sent out as soon as possible.

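### Protocol Section 17.2.1: tier B's upper limit of <3×ULN leaves the rare patient with both Baseline enzymes at or above 3×ULN in neither DILI tier A nor tier B

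*Protocol*

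**What the plan says.** Protocol Appendix II works in two steps. Four laboratory triggers, or signs of hepatitis, send any patient for a retest whatever the Baseline. The test and retest are then checked against Criteria A, B or C in Section 17.2.1.

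- **Tier A** opens "For patients with ALT and/or AST <ULN at study start (Baseline Values"). Its enzyme criterion (A-a) is ALT or AST >3×ULN.
- **Tier B** opens "For patients with ALT and/or AST between ≥ULN and <3×ULN at study start (Baseline Values"). Its enzyme criterion (B-a) is ALT or AST >2×Baseline.
- Both tiers also list bilirubin >2×ULN (b), INR >1.5 unless anticoagulated (c), and clinical signs (d), all confirmed on repeat.
- **Criteria C**, the stopping rule, has no Baseline entry condition: C-a is an enzyme >5×Baseline; C-b is >10×ULN; C-c is "ALT or AST >3×Baseline (see Figure 3 for illustration) with 1 or more of the following" (bilirubin, INR or symptoms); C-d is "ALT or AST >Baseline with any 2 or more of the following".

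Baseline values for these rules "are determined by averaging the values obtained at Screening and Baseline/Day 1 to obtain the arithmetic mean". Exclusion criterion 6 in Section 4.2 removes only ALT or AST >3×ULN.

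Several actions depend on meeting a tier. Section 7.1.5 states: "AESIs of DILI will be defined as any DILI event that meets the criteria in" A, B or C of Appendix II. Section 17.2.1 sends for close monitoring and AESI reporting "Any suspected or confirmed DILI event, defined as events meeting the criteria in A, B, or C above". Section 17.2.2 keys the hepatitis work-up to the same criteria ("Follow-Up procedures for patient(s) who meet" A, B or C).

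Figures 2 and 3 illustrate the rules. Only their titles can be read here, and both refer to ALT ≤3×ULN at Baseline, not <3×ULN.

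**The concern.** The entry conditions of A and B should together cover everyone who can be randomized. Tier A needs at least one enzyme below ULN; tier B needs at least one from ULN to just under 3×ULN. A patient with both at or above 3×ULN satisfies neither, yet the eligibility rule does not clearly keep that patient out.

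Meeting A, B or C starts close monitoring, the viral and other work-up, 24-hour AESI reporting and blinded adjudication. SAP Section 10.7.7 takes AESIs from a CRF question, so the AESI tables inherit how sites read these criteria. The patients who lose triggers are those with the highest Baseline enzymes. Section 1.1.4 already reports four SAEs of mildly raised liver tests in this study, considered possibly related to study drug, although nothing links them to this gap.

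**Working it through.** The plan states no figure to reproduce; this is a check of classification logic. Enzymes and bilirubin are in ×ULN, and and/or is read as an inclusive or.

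**1. Coverage.** Each enzyme can be <1, 1 to <3, or ≥3, giving 3 × 3 = 9 ALT/AST combinations.

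| Baseline pair (either order) | Combinations | As written | Upper limit deleted |
|---|---|---|---|
| <1 and <1 | 1 | A | A |
| <1 and 1 to <3 | 2 | A and B | A and B |
| <1 and ≥3 | 2 | A | A and B |
| 1 to <3, both | 1 | B | B |
| 1 to <3 and ≥3 | 2 | B | B |
| ≥3, both | 1 | neither | B |

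One combination of nine is uncovered. Reading and/or as a strict and would be worse: only the two concordant pairs below 3 would be covered, leaving 9 − 2 = 7 uncovered.

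**2. Can it occur?** Exactly 3.0 is not excluded. For both enzymes, Screening 2.9 with Day 1 3.1 gives (2.9 + 3.1)/2 = 3.0, and Screening 2.8 with Day 1 3.4 gives (2.8 + 3.4)/2 = 3.1. Any route through a Day 1 value above 3 assumes that result is not known at randomization, which the documents do not settle.

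**3. What is left at Baseline 3.0/3.0.** Only Criteria C can be met:

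- C-a: 5 × 3.0 = 15, so >15
- C-b: >10
- C-c: 3 × 3.0 = 9.0, so >9.0 with one companion
- C-d: above Baseline with two companions

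An isolated enzyme rise first counts above 10. With one raised companion (bilirubin or INR) it first counts above 9.0. Isolated bilirubin or INR never counts.

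**4. Comparison with a near-identical patient.** Assumptions: Baseline bilirubin 0.8, no symptoms, INR normal unless shown, abnormalities confirmed on repeat. For Baseline 2.9/3.0, B-a on ALT is 2 × 2.9 = 5.8; with the limit deleted, B-a at 3.0/3.0 is 2 × 3.0 = 6.0.

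| On treatment | 3.0/3.0 as written | 2.9/3.0 as written | 3.0/3.0, limit deleted |
|---|---|---|---|
| Bilirubin 2.1 only | none | B-b | B-b |
| INR 1.6 only | none | B-c | B-c |
| ALT 6.1 only | none | B-a | B-a |
| ALT 8.0, bilirubin 2.1 | none | B-a, B-b | B-a, B-b |

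Still at 3.0/3.0 as written, ALT 9.1 with bilirubin 2.1 meets C-c, ALT 10.1 alone meets C-b, and ALT 8.0 with bilirubin 2.1 and INR 1.6 meets C-d.

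**The case against.** **The gap may be smaller than the text suggests.** B-a points to Figure 2, and the titles of both figures say ≤3×ULN, so exactly 3.0 may have been meant to fall in tier B. Above 3.0, footnote f of Table 1 requires a final eligibility check before randomization on Day 1, and exclusion 6 is not tied to Screening as the TSH criterion is, so a known high Day 1 result could exclude the patient. Both points have force and make the case rare. Neither repairs the text: the written limit is <3×ULN, the figures' ≤3×ULN would cover 3.0 but not 3.1, and nothing says that the Day 1 central result is available in time.

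**Safeguards remain.** This stands. A reader might infer that such a patient goes unmonitored; the documents do not support that. The retest triggers apply to everyone and already include enzymes ≥3×ULN. Section 5.3.2.1 sends these abnormalities to Appendix II and makes the investigator responsible for identifying DILI. Criteria C applies at any Baseline, and ordinary AE/SAE reporting continues. Symptoms are separately covered: Section 5.3.1 refers symptomatic patients to Appendix II, Section 17.2.2 item 4 requires stopping drug and a suspected-DILI evaluation when symptoms accompany raised laboratory values, and the end of Section 17.2.2 orders further tests for symptoms of hepatitis. Symptoms are therefore not counted in the gap. What the retest does not do is start A/B close monitoring or create an AESI, because its result is checked only against A, B or C.

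**Overlap.** A reader might also infer a second defect: a patient with one enzyme below ULN and the other at 1 to <3×ULN is in both tiers, whose enzyme thresholds differ. The documents do not support calling this an error. Sections 7.1.5 and 17.2.1 count an event that meets any one of A, B or C, so either tier suffices and the overlap errs towards more capture. A rule to separate the tiers would narrow capture; none is needed.

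**Conclusion.** The gap is real on the text and worth correcting, but small. One of nine Baseline combinations falls in neither tier. For it, confirmed isolated bilirubin >2×ULN, INR >1.5, or an enzyme rise up to 10×ULN meets no criterion; with one companion abnormality at Baseline 3.0, neither does an enzyme rise up to 9×ULN. The number of patients is not in the documents and is expected to be very small.

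This rests on the inclusive reading of and/or, the wording without sight of the figures, and, for Baseline values above 3.0, the Day 1 result being unknown at randomization.

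The consequence is incomplete close monitoring and DILI AESI capture for that patient. It would be wrong to infer a bias between arms: tier membership is fixed before treatment and no arm difference is shown. The primary ALP analysis is untouched. The sDILI table and Hy's law flags (SAP Section 12.6.3), the eDISH plot (SAP Section 12.6.4) and the IDMC's eDISH review do not use tiers A or B.

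**What to change.** In Section 17.2.1, delete the <3×ULN limit from tier B so that it covers any Baseline at or above ULN. B-a then applies at >2×Baseline (>6.0×ULN at Baseline 3.0), and B-b to B-d apply to these patients. One side effect is that patients with one enzyme below ULN and the other at or above 3×ULN move from tier A alone to both tiers, which only adds triggers. Check that Figures 2 and 3 match the revised limit.

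The cost is a few words in Appendix II and a memo to sites; no new tests are needed.

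SAP Section 12.4 describes the blinded data review as already held, so dosing may have ended. In that case, add one supportive AESI derivation that applies the corrected laboratory criteria to central-laboratory data already collected. Use the arithmetic-mean Baseline of Appendix II, not the geometric mean of SAP Section 10.1.1, and label the analysis post hoc if it is specified after unblinding.
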